Patients with stable angina with evidence for at least >10% perfusion defect (moderate to large ischemia) or patients with troponin-negative unstable angina.

Exclusion Criteria: A need for oral anticoagulation therapy; an increased risk of bradycardia, and concomitant therapy with a strong cytochrome P-450 inhibitors; surgery<4 weeks; The use of any thienopyridines prior to randomization; upstream use of GP IIb/IIIa inhibitors; bleeding diathesis or major bleeding episode within 2 weeks; thrombocytopenia; incessant chest pain; hemodynamic instability; NSTEMI as evidenced by elevation of troponin levels; renal failure with a serum creatinine >2.0 mg/dL; and anemia with HCT<30%.

Methods

In this study, 100 patients with stable angina or troponin negative unstable angina, will be randomized to ticagrelor loading dose versus clopidogrel loading dose and eptifibatide bolus only administrated before PCI. Platelet function testing will be performed at baseline, at 30 min post-loading dose, 2 h, and 4 h, and 24 h. All patients will be started on aspirin 81 mg prior to procedure . Heparin 60 units/kg will be administered intravenously before PCI. PCI will be performed in accordance with standard clinical practice. Please see Fig. 2, Design of the study below and Table 1.

Fig. 2

Blood Sampling for Platelet Function Testing

Blood will be collected from an antecubital vein into vacutainer tubes (Becton-Dickinson, Franklin Lakes, NJ) that contain 3.2% trisodium citrate for light-transmittance aggregometry. All measurements will be performed at the UAB thrombosis research laboratory.

Light-Transmittance Aggregometry

Platelet aggregation induced by ADP (5 and 20 μm), TRAP (10 and 20 μm) platelet-rich plasma will be measured with a Chronolog Optical Aggregometer (model 490-4D; Chronolog Corporation, Havertown, Pa). The final extent of aggregation, measured at 6 minutes after agonist addition, and the maximal extent of aggregation will be expressed as the percent change in light transmittance from baseline with platelet-poor plasma as a reference. Inhibition of platelet aggregation (IPA) will be calculated as follows:

$$\text{IPA}(\%) = 100\% \times \frac{\text{PA}_t - \text{PA}_b}{\text{PA}_b}$$

Where PA is platelet aggregation, b is predosing, and t is postdosing.

Statistical Analysis

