The present study is an exploratory trial to investigate the percent inhibition of platelet activity (%IPA) (measured by light-transmittance aggregometry) comparing the loading dose of ticagrelor

with loading dose of clopidogrel and 2 boluses of eptifibatide measured at all time-points. Since there are no preliminary data available, no power calculation was performed. Statistical analysis will be performed using the Statistical Package for Social Sciences, version 22.0, software package for Windows (SPSS, Inc., Chicago, Illinois). Data will be presented as mean \pm 1 SD or frequencies; a value of $P < 0.05$ will be considered statistically significant. %IPA of ticagrelor and 2 boluses of eptifibatide vs. loading dose of clopidogrel and 2 boluses of eptifibatide will be compared at all time-points using repeated measures ANOVA. Continuous variables will be compared between the 2 treatment groups with Student t test. For comparisons of categorical data, the Chi-Square test will be performed.

End-Points

The primary end point of the study is to compare %IPA induced by ADP at 2 h, in patients randomized to the loading dose of ticagrelor with loading dose of clopidogrel and 2 boluses of eptifibatide measured at 2 h post loading dose. Secondary endpoints of the study are to compare %IPA induced by ADP and TRAP in patients randomized to the loading dose of ticagrelor with loading dose of clopidogrel and 2 boluses of eptifibatide at all time-points. Other secondary outcomes include: 1) the occurrence of post-procedural myonecrosis comparing the 2 groups. Ischemic myonecrosis will be defined as elevated post-procedure troponin-1 level $>0.26 \mu\text{g/l}$; and 2) the rate minor (a fall in hemoglobin of 3 to $<5 \text{ g/dL}$) and major bleeding (a fall in the hemoglobin $>5 \text{ g/dL}$) between the groups.

Anticipated Findings

Since platelet inhibition with ticagrelor starts rapidly, we expect that %IPA at 2 h will be no significantly different than clopidogrel and eptifibatide bolus. In addition, since eptifibatide half-life is short, we expect that %IPA at 24 h will be higher with ticagrelor than clopidogrel and eptifibatide bolus.

We anticipate the results of the present study will set the stage for a large randomized trial comparing myonecrosis, stent thrombosis, death, myocardial infarction, bleeding, and costs in patients randomized to ticagrelor only vs. loading dose of clopidogrel and 2 boluses of eptifibatide.

Table 1: Schedule of treatment

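### Secondary outcome 2 (bleeding): report risk differences with intervals, use Fisher's exact test for sparse counts, and define the haemoglobin fall so that a transfusion cannot hide a bleed

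*Combined protocol and SAP*

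**What the plan says.** In the End-Points section, the second of the other secondary outcomes is the rate of minor bleeding, a haemoglobin fall of 3 to <5 g/dL, "and major bleeding (a fall in the hemoglobin" exceeding 5 g/dL). The section does not name the post-baseline sample that defines the fall.

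The Statistical Analysis section has no sentence specific to bleeding, so three general rules apply:
- Display: "Data will be presented as mean" with one SD, or as frequencies.
- Classes: "For comparisons of categorical data, the Chi-Square test will be performed".
- Continuous data: "Continuous variables will be compared between the 2 treatment groups with Student t test". This would permit an unadjusted comparison of haemoglobin, although haemoglobin change is not listed as an outcome.

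The significance limit is P<0.05. No risk difference, confidence interval, exact test or transfusion rule is given.

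Table 1 schedules Hgb/Hct at baseline, discharge and 4 weeks, with nothing between baseline and discharge. It does not list transfusion. Under Methods, 100 patients "will be randomized to ticagrelor loading dose versus clopidogrel loading dose and eptifibatide bolus only administrated before PCI"; the allocation ratio is not stated. Under Anticipated Findings, the results are meant to "set the stage for a large randomized trial comparing myonecrosis, stent thrombosis, death, myocardial infarction, bleeding, and costs".

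**The concern.** Three features of the plan combine badly for a rare outcome in a small trial.

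- **The test.** Chi-square relies on a large-sample approximation. With few events it can cross P<0.05 where an exact test does not, and with none it gives no result at all.
- **The summary.** A P value and two frequencies tell the planners of the larger trial little. They need a difference and the range of differences compatible with the data.
- **The definition.** A class defined only by a haemoglobin fall depends on which sample is used. Discharge is the only scheduled in-hospital value after the procedure. A patient who bleeds and is transfused before that sample may show little net fall and be counted as free of bleeding. A fall of exactly 5 g/dL lies outside both classes.

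At stake is the usefulness of the bleeding comparison for the next trial, and the risk that a chance split or a missed bleed is misread as a safety signal or as reassurance. The primary endpoint is not affected.

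**Working it through.** **Inputs.** From the documents: 100 randomised (Methods); P<0.05, the bleeding definitions and chi-square (Statistical Analysis and End-Points); the haemoglobin schedule (Table 1). Assumed: 1:1 allocation (50 per arm), two-sided testing, no dropout. The documents give no bleeding rates and no SD of haemoglobin change, so those are assumed over ranges. No power calculation was done, so there is no planned figure to reproduce.

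**1. How sparse the counts are.** With equal arms, the expected number of events per arm is (a+b)/2, which is below 5 whenever the total is under 10. The probability of that is at least 0.92 for true rates of 1% v 3%, 2% v 5% and 2% v 10%, and 0.45 for 5% v 15%. No events in either arm has probability 0.99^50 x 0.97^50 = 0.605 x 0.218 = 0.13 at 1% v 3%.

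**2. Chi-square against Fisher at 0/50 v 4/50.** Chi-square = 100 x (0 x 46 - 4 x 50)^2 / (50 x 50 x 4 x 96) = 4,000,000 / 960,000 = 4.17, so p=0.041. Fisher's exact p is 0.117. The expected count is 2 per arm.

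**3. Power of the class comparison (exact enumeration).**

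| True rates | Chi-square | Fisher |
|---|---|---|
| 1% v 3% | 4% | 0.2% |
| 2% v 5% | 9% | 1.5% |
| 2% v 10% | 38% | 19% |
| 5% v 15% | 39% | 24% |

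Neither test is informative by its P value alone.

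**4. Newcombe intervals.** These combine the Wilson limits (l, u) of each arm. For d = p1 - p2, the lower limit is d - sqrt[(p1-l1)^2 + (u2-p2)^2] and the upper is d + sqrt[(u1-p1)^2 + (p2-l2)^2].
- 0/50 v 0/50: the Wilson upper limit is 3.84/(50+3.84) = 0.071, so the interval is -7.1 to +7.1 points.
- 3/50 v 1/50: d = 4.0 points, interval -5.4 to +14.3 (chi-square p=0.31).
- 4/50 v 0/50: Wilson limits are 0.0315 to 0.1884 and 0 to 0.0713. Lower = 0.08 - sqrt(0.0485^2 + 0.0713^2) = -0.006; upper = 0.08 + 0.1084 = 0.188. The interval of -0.6 to +18.8 points includes zero, in line with Fisher and not with chi-square.

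**5. Transfusion.** Suppose transfusion raises the discharge value by 2 g/dL (assumed). Any true fall of 3 to <5 then shows as 1 to <3 and leaves the minor class; a true fall of 5 to <7 shows as 3 to <5 and moves from major to minor. In a simulation with 3 g/dL of extra fall in 2% v 10% of patients, SD of change 1.0 and mean background fall 0.8 g/dL, transfusing every bleeder cuts the mean difference from 3 x 0.08 = 0.24 to 1 x 0.08 = 0.08 g/dL. Power falls from 23% to 2% for a pooled fall of 3 g/dL or more, and from 16% to 7% for a t test on change.

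**6. Whether haemoglobin change would do better.** Noncentrality is shift / (SD x sqrt(2/50)) = shift / (0.2 x SD). Take SD of change 1.0 or 1.2 and SD of level 1.5. Then rho = 1 - SD^2/(2 x 1.5^2) = 0.778 or 0.680, and the adjusted SD = 1.5 x sqrt(1 - rho^2) = 0.943 or 1.100.

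| Uniform shift | Change | Baseline-adjusted |
|---|---|---|
| 0.6 g/dL | 70-84% | 77-88% |
| 0.3 g/dL | 24-32% | 27-35% |
| 0.2 g/dL | 13-17% | 15-18% |

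If the excess is instead a few large bleeds (3 g/dL in 2% v 10%, SD of change 0.8-1.5), power is 11-19% on change and 12-19% adjusted. The pooled class has 13-30% with a background fall of 0.8 g/dL. With no background fall, change is slightly ahead of the pooled class at SD 0.8 (19% v 15%) and SD 1.0 (15.7% v 14.8%). The ranking of the two measures therefore depends on inputs the documents do not supply.

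**The case against.** The plan contains no error here. Two haemoglobin-fall classes are a legitimate safety endpoint, the trial is declared exploratory with a pharmacodynamic primary endpoint, and bleeding is the last-listed secondary outcome. Intervals can be added when the results are written up. All of that stands, and it sets the grade. It does not answer the points on sparse counts and definition, which are best settled before the data are seen.

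A reader might infer that the classes should give way to haemoglobin change because change is far more powerful. The documents do not support that. The high powers require every patient in one arm to shift by 0.6 g/dL, and nothing in the protocol gives that mechanism or size. Its only haemoglobin evidence, the earlier 70-patient study of different regimens described in the background, reports no significant difference. Baseline adjustment itself narrows intervals by only about 5-13% for correlations of 0.5 to 0.8.

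The transfusion illustration is a worst case, with every bleeder transfused and a 2 g/dL gain. A pre-transfusion rule is also fragile: Table 1 schedules no sample between baseline and discharge, so the value used may be an unscheduled one or may not exist. That stands too. It is why a transfused patient without such a value must be counted separately and not given a fall of zero.

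**Conclusion.** The point holds as an optional improvement. The bleeding comparison rests on chi-square alone, which cannot be computed at 0 v 0 and is unreliable at the counts to be expected (0 v 4: p=0.041 against Fisher p=0.117). A risk difference with an interval is available in every case. The definition also leaves two gaps: a post-transfusion discharge value can hide a bleed, and a fall of exactly 5 g/dL is unclassified.

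The results assume 50 per arm, two-sided testing and no dropout. The counts used are illustrations, and the rates, SDs and transfusion effect are assumptions. The defect in chi-square at 0 v 0 and the unclassified value do not depend on the assumed rates. No claim is made that haemoglobin change is the more powerful measure.

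**What to change.** Replace the bleeding analysis by wording such as this:

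- The fall is baseline haemoglobin minus the lowest in-hospital post-procedure value up to discharge, using only values taken before any transfusion.
- Minor bleeding is a fall of 3 to <5 g/dL and major bleeding a fall of 5 g/dL or more. The pooled class is a fall of 3 g/dL or more.
- Each of the three is reported by arm with a risk difference and Newcombe 95% CI. Fisher's exact test replaces chi-square when an expected count is below 5.
- Transfusions are recorded. A transfused patient with no pre-transfusion post-procedure value is counted separately by arm, not as a zero fall.
- Optionally, haemoglobin change to discharge is compared by a linear model with baseline haemoglobin as covariate and reported as a mean difference with 95% CI. It is descriptive and supportive only.

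**Cost.** A few lines of SAP text, three intervals, at most one model and a transfusion field on the case report form. Design, sample size and primary analysis are unchanged. Fisher's test is conservative (19% against 38% power at 2% v 10%), so the interval should carry the message. The lowest in-hospital value depends partly on unscheduled samples, so the number of samples per patient is worth reporting by arm. Haemoglobin change also reflects fluids and the timing of discharge.

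### The bleeding classes leave a haemoglobin fall of exactly 5 g/dL unclassified and ignore transfusion, so on the scheduled samples a transfused bleed can be graded too low

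*Combined protocol and SAP*

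**What the plan says.** The End-Points section lists two further secondary outcomes after the platelet measures. The first is myonecrosis: "Other secondary outcomes include: 1) the occurrence of post-procedural myonecrosis comparing the 2 groups". The second is bleeding, in two classes. The minor class opens with "the rate minor (a fall in hemoglobin of 3 to" and ends strictly below 5 g/dL. The other class opens with "major bleeding (a fall in the hemoglobin" and starts strictly above 5 g/dL. Both bounds at 5 are strict.

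The definition does not say which samples give the fall or over what period. Transfusion is not mentioned anywhere in the document.

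Table 1 (Schedule of treatment) places haemoglobin and haematocrit at baseline, discharge and 4 weeks, with nothing in the procedure column. Troponin, by contrast, is taken every 8 hours in that column. Adverse events are assessed at the procedure, discharge and 4 weeks, but nothing links them to the bleeding classes.

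On analysis, the Statistical Analysis section says: "For comparisons of categorical data, the Chi-Square test will be performed". The threshold is P < 0.05. The Methods section gives a total of 100 patients and no allocation ratio.

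**The concern.** There are two gaps. First, the classes do not meet: a fall of 5.0 g/dL is too large for minor and not large enough for major.

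Second, the fall is taken without regard to transfusion. The patients most likely to be transfused are those who bled most. If the post-procedure value is the discharge sample, transfusion has already raised it, and the recorded fall is smaller than the bleed caused. The rule then tends to lower the grade of the events that the safety comparison most needs to count.

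The randomised regimens differ in the use of eptifibatide, and the background section raises bleeding as a reason for shorter glycoprotein inhibitor regimens. The plan also expects this study to prepare a larger trial whose listed outcomes include bleeding. Its counts may therefore be carried forward even though they are secondary here.

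**Working it through.** The plan derives no figure for bleeding, so there is nothing to reproduce. The check applies the written rule to given falls.

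**Inputs from the document.** Minor: 3 ≤ fall < 5 g/dL. Major: fall > 5 g/dL. Samples: baseline, discharge, 4 weeks.

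**Assumed input.** Rise in haemoglobin per transfused unit, r = 0.5, 1.0 or 1.5 g/dL. The document gives no figure.

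**Step 1: the boundary.** At a resolution of 0.1 g/dL:

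| Fall (g/dL) | Class |
|---|---|
| 2.9 | none |
| 3.0 | minor |
| 4.9 | minor |
| 5.0 | no class |
| 5.1 | major |

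Only the value 5.0 is affected.

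**Step 2: transfusion before the discharge sample.** Net fall = true fall − units × r. For a true fall of 6.0 with 2 units at r = 1.0: 6.0 − 2 × 1.0 = 4.0, which is minor. In the same way:

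| True fall | Units | Net fall at r = 0.5 / 1.0 / 1.5 | Class under the written rule | Class of the true fall |
|---|---|---|---|---|
| 6.0 | 1 | 5.5 / 5.0 / 4.5 | major / no class / minor | major |
| 6.0 | 2 | 5.0 / 4.0 / 3.0 | no class / minor / minor | major |
| 6.0 | 4 | 4.0 / 2.0 / 0.0 | minor / none / none | major |
| 5.5 | 2 | 4.5 / 3.5 / 2.5 | minor / minor / none | major |
| 4.0 | 2 | 3.0 / 2.0 / 1.0 | minor / none / none | minor |
| 7.0 | 1 | 6.5 / 6.0 / 5.5 | major / major / major | major |

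Any positive r reduces the fall, so the direction does not depend on the assumption. Whether the class changes does depend on it: the last row keeps its class throughout.

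**Step 3: effect on the comparison (illustrative counts).** Suppose arm A has 2 major and 2 minor bleeds, and arm B has 0 major and 1 minor.

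- If both majors are recorded as minor, the major difference goes from 2 − 0 = 2 to 0.
- The minor difference goes from 2 − 1 = 1 to 4 − 1 = 3.
- Total bleeding stays at 4 against 1.
- If instead one of arm A's minor bleeds drops to none, the minor difference goes from 1 to 0 and total bleeding from 4 to 3 in that arm.

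**Step 4: sensitivity to one patient (illustrative).** Assume 50 per arm and no continuity correction.

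- 4 against 0 events: χ² = 100 × (4 × 50)² / (50 × 50 × 4 × 96) = 4.17, p = 0.041.
- 3 against 0 events: χ² = 100 × (3 × 50)² / (50 × 50 × 3 × 97) = 3.09, p = 0.079.

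One reclassified patient can move the result across 0.05. With so few events the chi-square approximation is itself rough, so this shows fragility only.

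**The case against.** The strongest reply is that the plan never says it uses the net fall. It says only that there is a fall. Table 1 lists scheduled tests and does not state that only those values count, so an investigator could use a lower value from a clinically ordered sample. A serious bleed could also be recorded as an adverse event. This stands in part. A reader might infer that the plan prescribes the net fall; it does not. What the document supports is narrower: no transfusion term is given, and applying the rule to the samples that the plan schedules yields a fall reduced by transfusion.

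A reader might also infer that the error always shrinks the difference between arms. Step 3 shows otherwise for minor bleeding. Attenuation is to be expected for major bleeding, and for total bleeding when events leave both classes, provided transfusion practice is similar in the two arms.

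The gap at 5 g/dL may be a greater-than-or-equal sign lost in preparing the file, or loose drafting. That cannot be settled from the text and is a small matter either way.

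Finally, the outcome is secondary, and the plan calls the trial exploratory, with no power calculation. That limits the severity but does not make the rule correct.

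**Conclusion.** The point holds at low severity. As written, a fall of exactly 5.0 g/dL has no class. On the scheduled samples, a bleed transfused before discharge can be graded too low: a true 6.0 g/dL fall with 2 units becomes unclassified or minor across the assumed range of 0.5 to 1.5 g/dL per unit, and with 4 units minor or no bleed. The likely result is too few major bleeds and, where events drop to none, too few bleeds in total.

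The size of the effect in this trial cannot be stated. The document gives no bleeding rate, transfusion rate or rise per unit, so the examples show what can happen, not how often. Nothing here touches the primary end point, inhibition of ADP-induced aggregation at 2 h.

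**What to change.** In End-Points:

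- Make one bound at 5 g/dL inclusive, for example major as a fall of 5 g/dL or more, so that every fall of at least 3 g/dL has exactly one class.
- Define the fall as baseline minus each scheduled post-procedure value (discharge and 4 weeks), plus the units transfused between the two samples multiplied by a stated conversion. State that the larger fall decides the class.
- Add units transfused, with dates, to the data collected.
- Report a fall to the lowest clinically ordered value only as a sensitivity analysis. It should not replace the scheduled values: an in-hospital lowest value would leave out the 4-week sample, and unscheduled sampling could differ between arms, since no blinding is described.

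The cost is a few lines of text and one extra data item, which Table 1 does not now contain. Some events will move to a more severe class, and the chosen conversion is itself an assumption, so the uncorrected fall should be reported alongside. No visit, blood sample or treatment changes.
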